8.9 Quality Control

C

Quality Control Guidelines and Procedures

This study will follow all applicable international and local quality regulations, including GPP. AstraZeneca standard operating procedures will also be used to ensure the quality of the data and study. These procedures include internal quality audits, rules for secure and confidential data storage, methods to maintain and archive project documents, quality control procedures for study monitoring, standards for writing a statistical analysis plan, and requirements for senior scientific review.

Data Quality Assurance

- Vaccination sites and study personnel must maintain accurate documentation and must permit study-related monitoring, audits, IEC review, and regulatory agency inspections, and provide direct access to study documents.
- Monitoring details describing strategy (eg, risk-based initiatives in operations and quality such as Risk Management and Mitigation Strategies and Analytical Risk-Based Monitoring), methods, responsibilities and requirements, including handling of noncompliance issues and monitoring techniques, are provided in the Site Monitoring Plan.
- The Sponsor assumes accountability for actions delegated to other individuals (eg, CROs).
- In-person monitoring of vaccination sites will only be performed if a specific cause requires investigation.
- Records and documents, including signed informed consent forms, pertaining to the conduct of this study must be retained by the Sponsor or designee for 5 years after study completion unless local regulations or institutional policies require a longer retention period. No records may be destroyed during the retention period without the written approval of the Sponsor. No records may be transferred to another location or party without written notification to the Sponsor.

Audits and Inspections

The Sponsor or designee may conduct a quality assurance assessment and/or audit of study records, and the regulatory agencies may conduct a regulatory inspection at any time during or after completion of the study.

8.10 Limitations of the Research Methods

Limitations of the research methods and how they are addressed by the study design are summarised in Table 4.

CCI

Table 4Study Limitations and Mitigations

Potential limitation	Reason for potential limitation	Rationale or mitigation
Study population lim	itations	
Uncertain enrolment	The status of the COVID-19 pandemic, availability of other vaccines, and the social and political environment at each location will impact recruitment and follow-up of vaccinated volunteers. The uncertainty of the situation and the highly dynamic environment can hinder enrolment forecasts.	Will evaluate enrolment on an ongoing basis and expand study to additional countries if needed.
Sampling bias	Some subgroups (ie, vulnerable persons and the elderly) may be over-represented in the study population, as compared to the general population who will receive the vaccine in the future.	As this study aims for at least 50% of participants \geq 65 years, potential bias towards older persons is a benefit. However, the ability to enrol sufficient participants \geq 75 years or \geq 80 years will depend on how many elderly individuals are still waiting to receive a vaccine or have chosen not to vaccinate yet due to vaccine hesitancy or local guidance when the study begins.
Selection bias	Self-enrolment of participants in the study after vaccination.	To reduce selection bias, the study includes digital and non-digital participation options, an option to use a proxy, and a range of vaccination site types where recruitment will take place.
Overall study design	limitations	
Unknown confounders	Sources of unmeasured and residual confounding could include socioeconomic factors, lifestyle factors (including exercise, diet, etc), and healthcare-seeking behaviour.	In this non-interventional surveillance study, the benefit of additional personal information needed to be weighed against the burden on participants' time and privacy.
Lack of internal comparator	While an internal comparison (ie, a cohort unexposed to any COVID-19 vaccine) is preferable, it was deemed not feasible.	 An internal comparator was not feasible because: Unethical to include volunteers that could be discouraged from vaccination Selection bias of volunteers who opt out of vaccination could result in different risk of outcomes An additional cohort would prolong study delivery
Recall bias	This study will permit enrolment remotely up to 28 days after the first vaccine dose and will only periodically remind participants to report outcomes, introducing the possibility of recall bias.	 The following study elements address recall bias: The primary analysis will be limited to participants who enrolled within 7 days of their first vaccine dose. Participants must complete the scheduled questionnaires within certain time windows.
Misclassification of events	Participants could self-report events inaccurately.	Study personnel will follow up to confirm as many event details as possible using medical records, as described in Section 10.2.

Table 4Study Limitations and Mitigations

Potential limitation	Reason for potential limitation	Rationale or mitigation
Failure to report events due to incapacity	Primary method of reporting outcomes is self-reporting	All participants will be asked to provide an emergency contact when they enrol. As described in Section 8.3.3, if a participant seems lost-to-follow-up, study personnel will reach out to the emergency contact and/or perform a search for vital status information.
Data analysis limitat	ions	
Generalisability	Point estimates and confidence intervals resulting from the analyses should only be interpreted as indications and not as reflective of a 'true' underlying estimand because of the limitations of conducting a study during an ongoing pandemic. This may impact the interpretation of the results as well as the ability to generalise the results to post-pandemic circumstances.	Will be considered for final analysis.
Missing data	Loss of participants in follow-up and/or missing data are limitations inherent in all primary data collection observational studies. In this non-interventional, observational study, participants may not respond to all prompts and may not complete the full 18-month follow-up period.	See Section 8.8 for planned handling of missing values in the analyses.
Risk assessment analyses	It is unclear how efficient risk assessment analyses will be during the COVID-19 pandemic given the impact of COVID-19 on general healthcare seeking behaviour. This may change over time as COVID-19 activity decreases. Paradoxically, increased outcomes may then be observed as vaccination coverage increases and COVID-19 decreases. Trends may be challenging to interpret in this changing healthcare-use environment, confounded by vaccine and other treatment/prevention measures.	Will be considered for final analysis.
Detection of rare events	Some rare events may not be detected in a sample size of 15,000.	Data from this study may be used in a pooled analysis or meta- analysis combining data from similar studies in different regions, for an overall enrolment of at least 30,000 across the studies.

AESI, adverse event of special interest.

CCI

8.11 Other Aspects

Study Governance and Committees

A Scientific Committee will be set up to support and oversee the study and will be governed by a charter detailing responsibilities and processes.

Other teams and committees will be established as needed.

9. **PROTECTION OF HUMAN SUBJECTS**

9.1 Ethical Conduct

Independent Ethics Committee approval will be obtained in accordance with applicable national and local regulations.

This study will be conducted in accordance with International Society for Pharmacoepidemiology Guidelines for Good Pharmacoepidemiology Practices (ISPE 2015) and applicable regulatory requirements including the European Medicines Agency Guideline on Good Pharmacovigilance Practices: Module VIII – Post-Authorisation Safety Studies (EMA 2017).

The Sponsor will also adhere to the general principles of transparency and independence in the European Network of Centres for Pharmacoepidemiology and Pharmacovigilance (ENCePP) Code of Conduct (ENCePP 2018). The ENCePP Checklist for Study Protocols is located in Appendix B.

9.2 Informed Consent

A signed and dated electronic or written informed consent will be obtained before any participant data is collected for the study. Electronic consent will be an option where permitted.

For vaccine recipients who choose to enrol in-person at a study site, if a study coordinator is present, the coordinator will ensure they are given full and adequate information about the nature and purpose of the study. They will be given the opportunity to ask questions and allowed time to consider the information provided. For vaccine recipients who choose to enrol remotely, similar information will be available electronically and the call centre will be available to answer questions.

All participants will need to consent to requests for their medical records (paper and electronic) to further evaluate safety events.

Participants vaccinated with AZD1222 during pregnancy or up to 45 days before estimated date of conception will be asked to follow outcomes in their child for up to 12 months after birth. Breastfeeding participants will also be asked to follow-up on the health of their child. If

any follow-up requires access to a child's medical records, consent will be requested from the participant and may be requested from the child's other parent/caregiver, depending on local requirements.

9.3 Participant Data Protection

Data privacy and confidentiality practices will abide by local rules and will be subject to review by local IECs prior to the start of the study.

Participants will be assigned a unique identifier code by the digital platform. Any participant records or datasets that are transferred to the Sponsor will contain the identifier only. No information that could make the participant identifiable will be transferred to the Sponsor.

Participants will be informed that their personal study-related data will be used by the Sponsor in accordance with local data protection law. The level of disclosure and use of their data will be explained to participants in the informed consent. The participants will be informed that their medical records may be examined by authorised personnel appointed by the Sponsor, by appropriate IEC members, and by inspectors from regulatory authorities.

As part of the study onboarding steps, participants will need to choose if they are planning to use a proxy to act on their behalf in the study and provide their contact information. Participant proxies who use the study digital solutions will create a separate account that will be linked to the participant's account.

9.4 Registration of Study on Public Websites

The study will be registered in the ENCePP EU Register of Post-Authorisation Studies after protocol approval and before the study implementation commences.

10. MANAGEMENT AND REPORTING OF ADVERSE EVENTS/ ADVERSE REACTIONS

10.1 Definitions

10.1.1 Adverse Events

An AE is the development of any unfavourable and unintended sign, symptom, or disease temporally associated with the use of a medicinal product, whether or not related to the medicinal product. The term AE is used to include both serious and non-serious AEs and can include a deterioration of a pre-existing medical occurrence.

10.1.2 Serious Adverse Events

An SAE is an AE that fulfils one or more of the following criteria: results in death, is immediately life-threatening, requires in-patient hospitalisation or prolongation of existing hospitalisation, results in persistent or significant disability or incapacity, is a congenital

abnormality or birth defect, or is an important medical event that may jeopardise the participant or may require medical treatment to prevent one of the outcomes listed above.

Life-threatening: 'Life-threatening' means that the participant was at immediate risk of death from the AE as it occurred, or it is suspected that use or continued use of the product would result in the participant's death. 'Life-threatening' does not mean that had an AE occurred in a more severe form it might have caused death (eg, hepatitis that resolved without hepatic failure).

Hospitalisation: Outpatient treatment in an emergency room is not in itself an SAE, although the reasons for it may be (eg, bronchospasm, laryngeal oedema). Hospital admissions and/or surgical operations planned before or during a study are not considered AEs if the illness or disease existed before the participant was enrolled in the study, provided that it did not deteriorate in an unexpected way during the study.

Important Medical Event or Medical Treatment: Medical and scientific judgement should be exercised in deciding whether a case is serious in situations where important medical events may not be immediately life-threatening or result in death, hospitalisation, disability or incapacity but may jeopardise the participant or may require medical treatment to prevent one or more outcomes listed in the definition of serious. These should usually be considered as serious.

10.1.3 Medically-attended Adverse Events Following Immunisation

A medically-attended AEFI is a new or worsening health problem or symptom following immunisation, resulting in a consultation with a medical doctor, an emergency room visit, or hospitalisation. A consultation with a medical doctor can be remote (by phone or video) or can be an in-person visit.

10.1.4 Adverse Events of Special Interest

Adverse events of special interest are events of scientific and medical interest specific to the further understanding of the safety profile of a product and require close monitoring. An AESI can be serious or non-serious. A list of AESIs for AZD1222 was developed for the AZD1222 Risk Management Plan and will be followed for this study.

Table 5 lists the AESIs for AZD1222. The AESI list will be reviewed on an ongoing basis and the EU Risk Management Plan and the list for this study will be updated accordingly.

Body System/Classification	AESI or AESI Medical Concept		
Other system	Vaccine-associated enhanced disease (VAED), including vaccine associated enhanced respiratory disease (VAERD) ^a		
	Multisystem inflammatory syndrome in children		
	Sudden death		
Immunological	Autoimmune thyroiditis		
	Anaphylaxis		
Respiratory	Acute respiratory distress syndrome (ARDS)		
Neurologic	Guillain-Barré syndrome		
	Peripheral neuropathy and polyneuropathy		
	Multiple sclerosis, transverse myelitis, and other demyelinating disorders		
	Optic neuritis / neuromyelitis optica spectrum disorder		
	Non-infectious encephalitis (inc. acute disseminated encephalomyelitis) / non-infectious encephalopathy		
	Myasthenia gravis		
	Bell's palsy		
	Seizure disorders (inc. febrile)		
	Narcolepsy		
Cardiovascular system	Myocarditis/pericarditis		
	Myocardial infarction		
	Postural orthostatic tachycardia syndrome		
Circulatory	Thrombocytopaenia		
system/Haematological	Stroke and other cerebrovascular events, venous thromboembolism		
Renal	Acute kidney injury		
Gastrointestinal	Acute liver injury		
	Acute pancreatitis		
Musculoskeletal system	Acute aseptic arthritis		
	Fibromyalgia		
	Rhabdomyolysis		
General	Chronic Fatigue Syndrome/myalgic encephalomyelitis/postviral fatigue syndrome		
Pregnancy/Foetal/Neonatal	Pregnancy outcome – Maternal ^b		
	Pregnancy outcome – Neonates ^b		
Skin	Erythema multiforme		

Table 5Adverse Events of Special Interest for AZD1222

^a The case definition for VAED, including VAERD will follow the Brighton Collaboration Case Definition (Munoz et al 2021).

^b Additional information about the case definitions and preferred terms for these AESI medical concepts is provided in the EU Risk Management Plan and/or will be included in the Statistical Analysis Plan or other study documentation.
 AESI, adverse event of special interest, EU, European Union.

10.1.5 Adverse Drug Reaction

An adverse drug reaction (ADR) is a response to a medicinal product which is noxious and unintended. Response in this context means that a causal relationship between a medicinal product and an AE is at least a reasonable possibility. An ADR, in contrast to an adverse event, is characterised by the fact that a causal relationship between a medicinal product and an occurrence is suspected.

In this study, causality information will be requested from the HCP for all SAEs, AESIs, and medically-attended AEFIs. Study personnel will make a causality assessment for those events, considering the input from the HCP. For events without an HCP contact, study personnel will assess the events based on details provided from the participants.

10.1.6 COVID-19 Diagnosis and Lack of Efficacy

A COVID-19 diagnosis is defined as virologically-confirmed SARS-CoV-2 (eg, reverse transcription polymerase chain reaction [RT-PCR]) and:

- At least 1 symptom of COVID-19 disease (eg, objective fever [defined as ≥ 37.8 °C], cough, shortness of breath, anosmia, or ageusia) or
- COVID-19 diagnosis stated/provided by the physician.

In this study, lack of efficacy is defined as the occurrence of COVID-19 caused by SARS-CoV-2 in a person who is appropriately and fully vaccinated following an incubation period of \geq 15 days following the second dose of the vaccine.

10.2 Collection and Assessment Process for Adverse Events

Adverse events will be collected from the time of informed consent through 18 months post-first dose for participants. However, among pregnant women, follow-up will continue for 12 months after the birth of the child or until 24 months post-first dose of the last participant enrolled, whichever happens first.

Participants will receive timed notifications via push notification, email, or phone call asking for any new or worsening health issues that have resulted in consultation with a medical doctor, an emergency room visit or hospitalisation, or a significant or long-term disability or incapacitation.

Participants can also submit unprompted AE information at any time though the app, web portal, or call centre. All AEs collected during this study will be considered solicited AEs, regardless if they were prompted or unprompted.

If a participant indicates a new or worsened health problem, the participant will be asked additional questions about the issue, intensity, treatment, and outcome. Adverse events collected for this study, both prompted and unprompted, will focus on the events of interest for the study assessments and analyses: SAEs, AESIs, and medically-attended AEFIs, including COVID-19 infections. Should other AE types, however, be reported, these will also be collected and managed accordingly and presented in the study report.

All collected events will be immediately available to study personnel in the investigator dashboard, where new events will be flagged. Study personnel will then validate the cases, request medical records, and assess seriousness and causality with input from HCPs and the medical records (Figure 2).

Study personnel will confirm all collected AEs with the participant, the proxy, the emergency contact, and/or through the review of medical records. If the participant received care from an HCP aside from their primary care physician, study personnel will follow up to obtain contact information for that HCP to permit a medical record request. Follow-up for AESIs with the HCP will include the completion of a targeted safety questionnaire. The adjudication committee can be consulted for advice on whether any reported non-serious symptoms or events may be a suspected AESI and will also adjudicate select AESIs (Section 10.6).

Certain situations require collection and reporting to the Sponsor, regardless of whether the situation was related to an AE: exposure to the product during pregnancy, exposure to the product while breastfeeding, overdose, medication error, off-label use issue, drug abuse, drug misuse, occupational exposure, product quality complaints/issues, and lack of efficacy. For lack of efficacy definition, refer to Section 10.1.6.

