7. RESEARCH QUESTION AND OBJECTIVES

The purpose of this study is to assess the safety and tolerability of AZD1222 in adults vaccinated in real-world settings. Table 2 lists the study objectives and outcome measures.

Table 2	Study Objectives and Outcome Measures
---------	---------------------------------------

Objective	Outcome measure(s)
Primary objective	
To estimate the incidence of SAEs, AESIs, and medically-attended AEFIs after at least one IM dose of AZD1222 for 3 months after vaccination.	 Serious adverse events Adverse events of special interest Medically-attended AEFIs
Secondary objectives	
To estimate the incidence of SAEs, AESIs, and medically-attended AEFIs after at least one IM dose of AZD1222 for up to 18 months after vaccination.	 Serious adverse events Adverse events of special interest Medically-attended AEFIs
To estimate the incidence of SAEs, AESIs, and medically-attended AEFIs after at least one IM dose of AZD1222 in participants by age group.	 Serious adverse events Adverse events of special interest Medically-attended AEFIs
To estimate the incidence of SAEs, AESIs, and medically-attended AEFIs after at least one IM dose of AZD1222 in participants with select comorbidities.	 Serious adverse events Adverse events of special interest Medically-attended AEFIs
To estimate the frequency of select pregnancy outcomes in women vaccinated with AZD1222 during pregnancy or within 45 days of the estimated conception date.	 Events within the AESI medical concept "Pregnancy outcome – Maternal", including: Spontaneous abortions Stillbirths Preterm births

Table 2Study Objectives and Outcome Measures

Objective	Outcome measure(s)
To estimate the frequency of select outcomes at birth and	Events within the AESI medical concept
up to 12 months of age in neonates/infants born to	"Pregnancy outcome – Neonates", including:
mothers vaccinated with AZD1222 during pregnancy or	Major congenital malformations
within 45 days of the estimated conception date.	Small for gestational age
Exploratory objectives	
CCI	CCI
CCI	CCI
CCI	CCI
Serious adverse events, AESIs, and medically-attended AEFIs are of	
AE, adverse event; AEFI, adverse event following immunisation; A	
; CCI ; IM, intramuscular	; CCI

8. **RESEARCH METHODS**

; SAE, serious adverse event.

8.1 **Definitions**

In this protocol, the following terms are used as defined here:

Participants: Individuals who have enrolled in the study.

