8.2 Study Design

This is a Phase IV real-world, observational, non-interventional, prospective cohort study of adults who receive the AZD1222 vaccine. Vaccine recipients \geq 18 years old will be recruited

for the study at vaccination sites in Germany, France, Spain, and Sweden. Awareness of the study may be raised through social media and traditional media (television, print, and radio).

In this study, vaccination sites will not act as traditional study investigators and will not be responsible for participant screening or safety follow-up. Rather, participants will self-enrol in the study using the study app, web portal, or call centre and will submit answers to study questionnaires using those methods. Event follow-up and assessment, where needed, will also be performed remotely by study personnel. The digital platform will also include an investigator dashboard where investigators and selected study personnel can view and track, in real time, all adverse events (AEs) submitted. Role-based permissions will ensure only authorised personnel can view identifying confidential data like participant names.

Participants will enrol in the study after vaccination with AZD1222. Enrolment is permitted within 28 days of the first dose of AZD1222 and can be completed at the vaccination site or remotely. If a vaccine recipient chooses to enrol in the study at the vaccination site, a study research coordinator may be present and can assist by:

• Providing information about the study.

SCI

- Explaining the study participation options: study app, web portal, or telephone communication with the call centre.
- Assisting the participant with the informed consent process.
- Checking if participants meet the eligibility criteria and providing vaccination details.
- Recording contact information for the participant, the emergency contact (in case of apparent loss to follow-up), and the participant's proxy, if needed.
- Providing the proxy with instructions on how to assist the participant with reporting.

For vaccine recipients who would prefer to enrol remotely at a later date, up to 28 days after the first vaccine dose, a study information brochure will be available that includes instructions to remotely enrol (including electronic informed consent completion, where permitted) and their vaccination details (if a vaccination card was not already provided).

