Primary and secondary analyses. The primary analysis will only include participants who enrolled within 7 days of vaccination with the first dose of AZD1222. All AEs collected, regardless of seriousness, will be tabulated. The cumulative incidence of SAEs, AESIs, and medically-attended AEFIs will be computed as the proportion of participants who reported an event among all AZD1222 vaccinated participants who completed each study-defined follow-up interval as well as among all AZD1222-vaccinated participants regardless of completion status, in combination with corresponding patient-years.

Where feasible, incidence rates will be calculated (in person-years), both by dividing by number of person-years, as well as by taking into account death as a competing event and withdrawal from the study/loss-to-follow-up as a censoring event (using cumulative incidence). Kaplan-Meier curves will be used for this analysis where appropriate.

Summaries of SAEs, AESIs, and medically-attended AEFIs by intensity, seriousness, and relatedness will also be presented.

In the pregnancy sub-cohort, the prevalence of pregnancies that resulted in live births, spontaneous abortions, and stillbirths will be summarised along with any other pregnancy outcomes reported within the AESI medical concept of Pregnancy Outcomes - Maternal. Infant outcome measures will also by summarised by the prevalence of events in the AESI medical concept of Pregnancy Outcomes – Neonates, including small for gestational age and major congenital malformations.

Additional Supportive Analysis. To support safety signal evaluation, a risk assessment will be conducted for AESIs using background event rates established through the ACCESS project or another source (Meurs and Kant 2020, ACCESS 2020). To further enhance background rate identification, additional literature review will be conducted if ACCESS data is insufficient or unavailable. Appropriate risk windows will be estimated for these analyses

and counts of AESIs that occurred within the prespecified risk window will be compared against expected values using sequential testing. Where appropriate, analyses will be stratified by sex and age. To assess whether larger risks can be found based on bias, the background rates based on the external sources will be evaluated as they are and with additional scenarios.

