 - As participants can enrol in the study within 28 days of their initial vaccination, it will also be evaluated whether the AE risk for participants enrolling in the days and weeks after vaccination differs from the risk for participants enrolling immediately after vaccination. A sensitivity analysis will be performed that excludes subjects enrolled more than 2 days after the date of vaccination.
 - Participants who report pregnancy at the time of vaccination or an estimated date of conception within 45 days of vaccination will be included in the analyses for pregnant women. Sensitivity analyses will consider time windows less than 45 days.
 - Sensitivity analyses will evaluate the relationship between sex and loss-to-follow-up and the relationship between age and loss-to-follow-up.

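### Adverse-event collection starts at consent while incidence is counted from dose 1, and the protocol does not settle whether events in between count

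*Protocol*

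**What the plan says.** **Start of collection.** Section 10.2: "Adverse events will be collected from the time of informed consent through 18 months post-first dose for participants". Section 9.2 agrees: "A signed and dated electronic or written informed consent will be obtained before any participant data is collected for the study".

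**Gap after dose 1.** Section 8.2: "Enrolment is permitted within 28 days of the first dose of AZD1222 and can be completed at the vaccination site or remotely". Section 8.8 narrows this for the main result: "The primary analysis will only include participants who enrolled within 7 days of vaccination with the first dose of AZD1222". It adds one stricter check: "A sensitivity analysis will be performed that excludes subjects enrolled more than 2 days after the date of vaccination".

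**Period and denominator.** The primary objective in section 7 is: "To estimate the incidence of SAEs, AESIs, and medically-attended AEFIs after at least one IM dose of AZD1222 for 3 months after vaccination". Under section 8.8, cumulative incidence is computed among those who completed each follow-up interval and also "among all AZD1222-vaccinated participants regardless of completion status, in combination with corresponding patient-years". The same section treats death as a competing event and withdrawal or loss as censoring. It does not mention late entry.

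**AESI risk assessment.** Section 8.8: "counts of AESIs that occurred within the prespecified risk window will be compared against expected values using sequential testing". The protocol gives no length or origin for the risk windows and no start for the expected person-time. The 7-day limit is stated for the primary analysis and is not extended to this one.

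**Text pointing the other way.** Table 4 (section 8.10) lists enrolment up to 28 days after the dose as a source of recall bias, which implies that earlier events might be recalled and reported. Section 10.1.3 defines a medically-attended AEFI from immunisation, not from consent. The eligibility criteria (8.3.2.1) secure access to medical records from the time of vaccination.

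**The concern.** The objective's clock starts at dose 1, and collection starts at consent. If section 10.2 is applied literally, the days in between contribute no events, yet the participant counts in full in the denominator. That is left truncation without correction. If the events are instead recalled and counted, a different problem arises: people who had an event may be more likely to enrol. Someone who dies before consent cannot enrol under either reading, although sudden death is a listed AESI (Table 5).

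Early, acute events are the most exposed. Section 6.2 names anaphylaxis as an important potential risk, and the 2-day sensitivity analysis still leaves days 0 to 2 partly unobserved. The planned comparison of later with immediate enrollees does not resolve this: under the literal reading, later enrollees have fewer early events by construction. The example background-rate multipliers (1.2, 1.5 and 2.0) only raise the expected count, so they would add to any downward bias in the observed-to-expected ratio.

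**Working it through.** **Inputs from the protocol.** N = 15,000; latest enrolment day 2 (sensitivity analysis), 7 (primary analysis) or 28 (whole cohort); incidence period 3 months.

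**Assumptions, because the protocol gives no figures.** 3 months = 91 days (the nearest scheduled contact, week 14, is 98 days); the distribution of enrolment delay; risk-window lengths; the shape of onset times.

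**1. The plan's own figure.** The maximal half-width for a proportion is 1.96 × √(0.25/15,000) = 0.0080, which reproduces the stated ±0.8%. It does not depend on this point.

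**2. Share of 3-month events lost if events before consent are not counted, constant hazard.** Share = mean delay / 91.

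| Enrolment | Uniform over the range | All on the last day |
|---|---|---|
| Days 0–2 | 1/91 = 1.1% | 2/91 = 2.2% |
| Days 0–7 | 3.5/91 = 3.8% | 7/91 = 7.7% |
| Days 0–28 | 14/91 = 15.4% | 28/91 = 30.8% |

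With 98 days, the second row becomes 3.6% and 7.1%, and the third 14.3% and 28.6%.

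**3. Acute events.** For a 1-day window and uniform enrolment, the observable share is the mean of max(1 − delay, 0). Over days 0–2 this is ½ × ½ = 25%. Over days 0–7 it is 1/7 × ½ = 7.1%. For events with exponential onset (mean 3 days) in a 28-day window, the share kept is about (3/7) × (1 − e^(−7/3)) = 39% with enrolment uniform over days 0–7. Over days 0–28 it is about (3/28) × (1 − e^(−28/3)) = 11%.

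**4. Observed/expected ratio (O/E) if expected counts run from vaccination.** Under a constant hazard and uniform delay, with no delay longer than the window, the multiplier is (W − mean delay)/W for window W.
- W = 28: (28 − 3.5)/28 = 0.875 for days 0–7, and (28 − 14)/28 = 0.50 for days 0–28.
- W = 42: 38.5/42 = 0.917 and 28/42 = 0.667.

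Now take a true O/E of 2 in a 28-day window, with the excess following the early onset of step 3. The observed ratio is background kept plus excess kept: 0.875 + 0.387 = 1.26 for days 0–7, and 0.50 + 0.107 = 0.61 for days 0–28.

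**5. O/E if expected counts start at consent.** Under a constant hazard there is no bias by this route. With the early excess of step 4, the ratios are 1.262/0.875 = 1.44 and 0.607/0.50 = 1.21. Delayed entry removes the unobserved time but cannot recover an excess that occurred before consent.

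**6. If events before consent are counted.** The protocol gives no basis for a size. The bias would be upward to the extent that events prompt enrolment.

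**The case against.** The strongest reply is that section 10.2 only says when data gathering begins and does not exclude events with earlier onset. Besides the look-back text in Table 4, 10.1.3 and 8.3.2.1, section 8.4.3.1 records an onset date for every event, and the Table 3 note on the scheduled questions sets no start date for a new or worsening health issue. The participant questionnaires that might settle the matter (Appendix C) are not in the text available, and that cannot count against the plan. This stands. A reader might infer that gap events are excluded by rule and that incidence is therefore certainly too low. The protocol does not support that, and the direction depends on the reading.

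A reader might also infer that signal detection is certainly biased toward no signal. That does not follow either. The origin of risk windows and expected person-time is unstated and may properly be set in the separate SAP.

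The delay is not ignored. Table 4 lists self-enrolment after vaccination as selection bias as well as late enrolment as recall bias. Section 8.8 has the 7-day limit, the 2-day sensitivity analysis and a comparison by enrolment timing. Many participants may consent on site, with almost no gap, so the last-day figures are worst cases.

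What the reply does not remove is the inconsistency. Whether gap events are ascertained is a collection rule, and an SAP cannot recover events that were never collected. Section 8.8 also already fixes a denominator of all vaccinated participants.

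**Conclusion.** The concern holds in conditional form. The protocol starts collection at consent, measures incidence from vaccination, and is inconsistent on whether events in between count.

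- **Not counted:** 3-month incidence is biased downward. With a constant hazard and a 91-day period, the loss is about 4% to 8% in the primary analysis and about 15% to 31% without the 7-day limit. It is far larger for acute events. The upper figures need everyone to enrol on the last permitted day.
- **Counted:** enrolment prompted by an event can bias incidence upward, by an amount the documents do not allow one to estimate.
- **Either way:** deaths before consent are missed.
- **Observed/expected:** the ratio is biased toward no signal if expected counts run from vaccination. If they run from consent and the hazard is roughly constant, there is no bias by this route. The enrolment-delay limit is not stated for this analysis.

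For slowly varying outcomes in the primary analysis the effect is modest. For events in the first days it is not.

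**What to change.** 1. Reconcile section 10.2 with Table 4, 10.1.3 and 8.3.2.1 by stating whether events with onset between dose 1 and consent are ascertained.
2. In section 8.8, use days since dose 1 as the time scale with delayed entry. The risk set, person-time and expected AESI counts then start at consent.
3. Flag any ascertained event with onset before consent and report it separately. Do not discard it.
4. State the origin of the risk windows, and apply the enrolment-delay restriction to the AESI risk assessment.
5. Report day 0–2 events in participants who consented on the day of vaccination, noting that events and deaths before consent remain unobservable.
6. Keep the 7-day limit and the 2-day sensitivity analysis.

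**Cost.** Protocol and SAP wording only: consent is dated, and vaccination and onset dates are already collected. There is slightly less person-time in the first days. Delayed entry also assumes that enrolment timing is independent of event risk. Self-enrolment puts that in doubt, so the assumption should be stated with the results.
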